**Figure 1 Study Design**

T: telephone contact; V: study visit

## End of Study

The end of the study is defined as follows:

- End of study in one country: last patient last visit (LPLV) and sites are closed.
- End of study globally: LPLV globally and all sites closed.

### 7.1.2 Schedule of Assessments

The schedule of assessments is presented in [Table 1](#).

**Table 1 Schedule of Assessments**

Study Activity	Screening Period		Treatment Period								Follow-Up
			Random-ization	Phone Contact	4 weeks	8 weeks	12 weeks	18 weeks	22 weeks	24 weeks	
Study Days	-56 – (-35) ±2	-28 – (-7) ±2	0	14 ±3	28 ±3	56±3	84±3	126 ±3	154 ±3	168 ±3	196 ±3
Visits	Clinic Visit 1	Clinic Visit 2	Clinic Visit 3	n/a	Clinic Visit 4	Clinic Visit 5	Clinic Visit 6	Clinic Visit 7	Clinic Visit 8	Clinic Visit 9/EOT a	Clinic Visit 10 b
Informed consent c	X										
Inclusion/exclusion criteria	X		X								
Demographics	X										
Concomitant medication d	X	X	X	X	X	X	X	X	X	X	X
Medical and surgical history	X		X								
Blood sampling for genetic testing e	X										
Physical examination including voluntary photography	X		X							X	
Skin examination	X		X		X		X			X	X
Vital signs f	X	X	X		X	X	X	X	X	X	X
eDiary: itching, scratching, and sleep scores g	Daily diary entry										
Clinical chemistry h	X		X		X	X	X	X		X	X
Hematology h			X		X	X	X	X		X	X
Urinalysis h		X					X			X	

Study Activity	Screening Period		Treatment Period								Follow-Up
			Random-ization	Phone Contact	4 weeks	8 weeks	12 weeks	18 weeks	22 weeks	24 weeks	
Study Days	-56 – (-35) ±2	-28 – (-7) ±2	0	14 ±3	28 ±3	56±3	84±3	126 ±3	154 ±3	168 ±3	196 ±3
Visits	Clinic Visit 1	Clinic Visit 2	Clinic Visit 3	n/a	Clinic Visit 4	Clinic Visit 5	Clinic Visit 6	Clinic Visit 7	Clinic Visit 8	Clinic Visit 9/EOT a	Clinic Visit 10 b
Serum bile acids i	X	X	X		X	X	X	X	X	X	X
INR		X			X		X		X		X
Autotaxin j			X		X					X	
p-C4 j			X		X					X	
AFP			X							X	
Fat-soluble vitamins A & E		X								X	
Fat-soluble vitamin D			X							X	
Abdominal Ultrasound			X							X	
Fibroscan ® (where available)			X							X	
QoL questionnaire (PedsQL)			X							X	
Patient/Caregiver/Clinician Global Impression of Change					X		X			X	
Patient/Caregiver/Clinician Global Impression of Symptoms			X		X		X			X	
Pregnancy test k	X k	X	X		X	X	X	X	X	X k	
Study drug dispensed l			X		X	X	X	X	X		

Study Activity	Screening Period		Treatment Period								Follow-Up
			Random-ization	Phone Contact	4 weeks	8 weeks	12 weeks	18 weeks	22 weeks	24 weeks	
Study Days	-56 – (-35) ±2	-28 – (-7) ±2	0	14 ±3	28 ±3	56±3	84±3	126 ±3	154 ±3	168 ±3	196 ±3
Visits	Clinic Visit 1	Clinic Visit 2	Clinic Visit 3	n/a	Clinic Visit 4	Clinic Visit 5	Clinic Visit 6	Clinic Visit 7	Clinic Visit 8	Clinic Visit 9/EOT a	Clinic Visit 10 b
Adverse events m	Continuous collection										
Study drug compliance				X	X	X	X	X	X	X	

AFP: alfa-fetoprotein; BMI: body mass index; eCRF: electronic case report form; eDiary: electronic diary; EOT: End of Treatment; ICF: informed consent form; INR: international normalized ratio; p-C4: plasma 7 $\alpha$  Hydroxy 4-cholesten-3-one; PedsQL: Pediatric Quality of Life Inventory; QoL: quality of life; RR: respiratory rate; s-BA: serum bile acid.

- a Must also be performed at the time a patient is prematurely withdrawn from the study. This visit is the same as Visit 1 in the extension protocol (Study A4250-008).
- b Assessments must be performed 28 days following the final dose of study drug. This visit is omitted if patients are entering Study A4250-008.
- c The ICF (and assent) must be signed before any study procedures are performed.
- d Past (within 1 month prior to Visit 1) and current medication will be documented in the eCRF.
- e Blood sample for genetic testing will be drawn for all patients. Genetic analysis will only be performed on a patient’s extracted DNA if previous the clinical genetic result is equivocal, unavailable, or unobtainable.
- f Includes blood pressure, pulse, RR, temperature, height (or length depending on age), and body weight (using a certified weight scale). BMI will be calculated.
- g Includes training on use of the device at Screening (Visit 1) and review of patient daily entries during 14 days prior to Clinic Visit 3 to determine eligibility.
- h See [Table 3](#) for detailed parameters.
- i Patients will fast (water intake only is permissible) for at least 4 hours prior to the collection of samples for s-BA. Exceptions can be made for infants, less than 12 months of age, if unable to fast for the full 4 hours. All s-BA results during the treatment period and follow-up will be blinded.
- j Samples will not be collected for patients  $\leq 10$  kg.
- k For girls who have reached menarche. Serum test at Visit 1; urine test at other visits. A serum pregnancy test will also be conducted at Visit 9 for patients entering Study A4250-008. If a urine pregnancy test is positive, a serum pregnancy test should be performed to confirm the pregnancy.
- l Study drug to be taken once daily on Day 1 through Day 167 as described in [Section 8.2](#).
- m Adverse event information will be collected from the time of signing of the ICF to study discontinuation.

### 7.1.3 Study Procedures and Assessments

#### 7.1.3.1 Screening Period (Days -56 to 0)

##### Day -56 to Day -35/Clinic Visit 1

Patients will undergo a Screening Visit up to 56 days prior to the planned first day of study treatment. Screening procedures and assessments are as follows:

- Obtain written informed consent
- Assess inclusion/exclusion criteria ([Section 7.2](#))
- Record demographics (age, full date of birth, gender, race, and ethnicity)
- Document concomitant medications
- Medical and surgical history (date of diagnosis of PFIC Types 1 or 2, prior investigational medications for PFIC, historical liver function test [LFT] values, any surgery performed, any other diagnosis, and historical liver biopsy data)
- Blood sample for genetic testing
- Collect, if available, past confirmatory clinical genetic laboratory report for PFIC1/PFIC2 and send to central reader for review
- Physical examination, including voluntary photography ([Section 10.2.5](#))
- Skin examination ([Section 10.2.5](#))
- Vital signs ([Section 10.2.6](#))
- eDiary training and compliance requirements; patients begin daily recording of pruritus using the eDiary ([Appendix 2](#))
- Clinical chemistry ([Section 10.2.1](#))
- s-BA ([Section 9.2.1](#))
- Serum pregnancy test for girls of who have reached menarche
- AE monitoring

##### Day -28 to Day -7/Clinic Visit 2

A second Screening Visit will be performed. Screening procedures and assessments are as follows:

- Review concomitant medications
- Vital signs ([Section 10.2.6](#))
- Albireo PRO/ObsRO eDiary review for itching, scratching, and sleep scores and compliance
- Urinalysis ([Section 10.2.1](#))

- s-BA ([Section 9.2.1](#))
- International normalized ratio (INR)
- Fat-soluble vitamins A and E
- Urine pregnancy test for girls of who have reached menarche
- AE monitoring

#### **7.1.3.2 Treatment Period (Day 0 to Day 168)**

##### **Study Day 0/Clinic Visit 3 (Randomization)**

At the randomization visit, the following assessments will be conducted:

- Review inclusion/exclusion criteria ([Section 7.2](#))
- Review concomitant medications, medical and surgical history
- Physical examination, including voluntary photography ([Section 10.2.5](#))
- Skin examination ([Section 10.2.5](#))
- Vital signs ([Section 10.2.6](#))
- Albireo PRO/ObsRO eDiary review for compliance and entrance criteria requirement (see Inclusion Criteria 4, [Section 7.2.1](#))
- Clinical chemistry and hematology ([Section 10.2.1](#))
- s-BA ([Section 9.2.1](#))
- Autotaxin and p-C4 (samples will not be taken for patients  $\leq 10$  kg)
- Fat-soluble vitamin D
- Alfa-fetoprotein (AFP)
- Abdominal ultrasound ([Section 10.2.7](#))
- Fibroscan®, where available ([Section 9.2.7](#))
- Administer QoL (Pediatric Quality of Life Inventory [PedsQL]) questionnaire
- Patient/caregiver/clinician complete the patient global impression of symptoms (PGIS)
- Urine pregnancy test for girls who have reached menarche
- AE monitoring
- Study drug is dispensed and patients are instructed to administer daily from Day 1

##### **Study Day 14 (Telephone Contact)**

A study nurse will contact the patient/caregiver by telephone for monitoring of the following:

- Review concomitant medications

- Albireo PRO/ObsRO eDiary review for compliance
- AEs
- Evaluation of study drug compliance

#### **Study Day 28 and Day 84/Clinic Visits 4 and 6**

The following procedures and assessments will be performed:

- Review of concomitant medications
- Skin examination ([Section 10.2.5](#))
- Vital signs ([Section 10.2.6](#))
- Albireo PRO/ObsRO eDiary review for compliance
- Clinical chemistry and hematology ([Section 10.2.1](#))
- Urinalysis (at Clinic Visit 6 only; [Section 10.2.1](#))
- s-BA ([Section 9.2.1](#))
- INR
- Autotaxin and p-C4 (at Clinic Visit 4 only; samples will not be taken for patients  $\leq 10$  kg)
- Patient/caregiver/clinician complete the patient global impression of change (PGIC) and PGIS
- Urine pregnancy test for girls who have reached menarche
- AE monitoring
- Evaluation of study drug compliance
- Study drug is dispensed

#### **Study Day 56 and Day 126/Clinic Visits 5 and 7**

The following procedures and assessments will be performed:

- Review of concomitant medications
- Vital signs ([Section 10.2.6](#))
- Albireo PRO/ObsRO eDiary review for compliance
- Clinical chemistry and hematology ([Section 10.2.1](#))
- s-BA ([Section 9.2.1](#))
- Urine pregnancy test for girls who have reached menarche
- AE monitoring
- Evaluation of study drug compliance

- Study drug is dispensed

#### **Study Day 154/Clinic Visit 8**

The following procedures and assessments will be performed:

- Review of concomitant medications
- Vital signs ([Section 10.2.6](#))
- Albireo PRO/ObsRO eDiary review for compliance
- s-BA ([Section 9.2.1](#))
- INR
- Urine pregnancy test for girls who have reached menarche
- AE monitoring
- Evaluation of study drug compliance
- Study drug is dispensed

#### **Study Day 168/Clinic Visit 9/EOT**

The last dose of study drug is taken in the morning the day before Clinic Visit 9, and the following procedures and assessments will be performed (also performed at the time a patient prematurely withdraws):

- Review of concomitant medications
- Physical examination, including voluntary photography ([Section 10.2.5](#))
- Skin examination ([Section 10.2.5](#))
- Vital signs ([Section 10.2.6](#))
- Albireo PRO/ObsRO eDiary review for compliance
- Clinical chemistry, hematology, and urinalysis ([Section 10.2.1](#))
- s-BA ([Section 9.2.1](#))
- Autotaxin and p-C4 (samples will not be taken for patients  $\leq 10$  kg)
- AFP
- Fat-soluble vitamins A, E, and D
- Abdominal ultrasound ([Section 10.2.7](#))
- Fibroscan®, where available ([Section 9.2.7](#))
- Administer PedsQL questionnaire
- Patient/caregiver/clinician complete the PGIC and PGIS

- Urine pregnancy test for girls who have reached menarche, or serum pregnancy test for girls continuing to study A4250-008
- AE monitoring
- Evaluation of study drug compliance

### 7.1.3.3 Follow-Up Period

#### Study Day 196/Clinic Visit 10

All patients not continuing into Study A4250-008 will return to the study site 28 days after Clinic Visit 9 or the last dose of study drug for the following assessments:

- Review of concomitant medications
- Skin examination ([Section 10.2.5](#))
- Vital signs ([Section 10.2.6](#))
- Albireo PRO/ObsRO eDiary review for compliance
- Clinical chemistry and hematology ([Section 10.2.1](#))
- s-BA ([Section 9.2.1](#))
- INR
- AE monitoring

## 7.2 Study Population

A total of 60 patients with clinical diagnosis of PFIC Type 1 or 2 that have been genetically confirmed will be randomized.

An attempt will be made to randomize a minimum of 10 patients from each age category (6 months to 5 years, 6 to 12 years, and 13 to  $\leq 18$  years).

A maximum of 5 patients that were treated in Study A4250-003 will be allowed to participate in this study.

### 7.2.1 Inclusion Criteria

1. A male or female patient, with clinical diagnosis of PFIC Type 1 or 2, between the ages of  $\geq 6$  months and  $\leq 18$  years at Visit 1 with a body weight above 5 kg
2. Patient must have genetic confirmation of PFIC-1 or PFIC-2 through identification of biallelic pathogenic variants in either the *ATP8B1* or *ABCB11* genes
3. Patient must have elevated s-BA concentration, specifically measured to be  $\geq 100$   $\mu\text{mol/L}$ , taken as the average of 2 samples 7 to 28 days apart (Visits 1 and 2) prior to randomization

4. Patient must have history of significant pruritus and a caregiver-reported observed scratching in the eDiary average of  $\geq 2$  (on 0 to 4 scale) in the 2 weeks prior to randomization
5. Patient and/or legal guardian must sign informed consent (and assent) as appropriate. Patients who turn 18 years of age (or legal age per country) during the study will be required to re-consent in order to remain in the study
6. Patients will be expected to have a consistent caregiver(s) for the duration of the study
7. Caregivers and age-appropriate patients ( $\geq 8$  years of age) must be willing and able to use an eDiary device as required by the study

### 7.2.2 Exclusion Criteria

1. Patient with pathologic variations of the *ABCB11* gene that predict complete absence of the BSEP function
2. Patient with past medical history or ongoing presence of other types of liver disease including, but not limited to, the following:
  - a) Biliary atresia of any kind
  - b) Benign recurrent intrahepatic cholestasis, indicated by any history of normal s-BAs
  - c) Suspected or proven liver cancer or metastasis to the liver on imaging studies
  - d) Histopathology on liver biopsy is suggestive of alternate non-PFIC related etiology of cholestasis
3. Patient with a past medical history or ongoing presence of any other disease or condition known to interfere with the absorption, distribution, metabolism (specifically bile acid metabolism), or excretion of drugs in the intestine, including but not limited to, inflammatory bowel disease
4. Patient with past medical history or ongoing chronic (i.e.,  $>3$  months) diarrhea requiring intravenous fluid or nutritional intervention for treatment of the diarrhea and/or its sequelae
5. Patient has a confirmed past diagnosis of infection with human immunodeficiency virus or other present and active, clinically significant, acute, or chronic infection, or past medical history of any major episode of infection requiring hospitalization or treatment with parenteral anti-infective treatment within 4 weeks of treatment start (study Day 1) or completion of oral anti-infective treatment within 2 weeks prior to start of Screening Period
6. Any patient with suspected or confirmed cancers except for basal cell carcinoma, and non-liver cancers treated at least 5 years prior to Screening with no evidence of recurrence

7. Patient with a past medical history of chronic kidney disease with an impaired renal function and a glomerular filtration rate  $<70$  mL/min/1.73 m^2
8. Patient with surgical history of disruption of the enterohepatic circulation excluding those who have undergone a successful reversal procedure that has permanently restored flow of bile acids from the liver to the duodenum
9. Patient has had a liver transplant or listed for liver transplant
10. Decompensated liver disease, coagulopathy, history or presence of clinically significant ascites, variceal hemorrhage, and/or encephalopathy
11. INR  $>1.4$  (the patient may be treated with Vitamin K intravenously, and if INR is  $<1.4$  at resampling the patient may be randomized)
12. Serum ALT  $>10 \times$  upper limit of normal (ULN) at Screening
13. Serum ALT  $>15 \times$  ULN at any time point during the last 6 months unless an alternate etiology was confirmed for the elevation
14. Total bilirubin  $>5 \times$  ULN at Screening
15. Patient suffers from uncontrolled, recalcitrant pruritic condition other than PFIC. Examples include, but not limited to, refractory atopic dermatitis or other primary pruritic skin diseases
16. Any patient who is pregnant or lactating or who is planning to become pregnant within 24 weeks of randomization
17. Sexually active males and females who are not using a reliable contraceptive method with  $\leq 1\%$  failure rate (such as barrier protection, hormonal contraception, intrauterine device, or complete abstinence) throughout the duration of the study (from signed informed consent through Follow-up, Visit 10).
18. Patient with a past medical history of alcohol or substance abuse will be excluded. Patient must agree to refrain from illicit drug and alcohol use during the study
19. Administration of bile acid or lipid binding resins and medications that slow GI motility (Refer to [Appendix 1](#) – Concomitant Medications Prohibited during the study)
20. Patient has had investigational exposure to a drug, biologic agent, or medical device within 30 days prior to Screening, or 5 half-lives of the study agent, whichever is longer
21. Patient who has been previously treated with an IBAT inhibitor whose pruritus has not responded to treatment
22. Any other conditions or abnormalities which, in the opinion of the investigator or Medical Monitor, may compromise the safety of the patient, or interfere with the patient participating in or completing the study

### 7.2.3 Withdrawal of Patients

Patients/caregivers will be informed that they have the right to withdraw from the study at any time, without prejudice to their medical care, and that they are not obliged to state their reasons.

Any withdrawal, and reasons for withdrawal, must be fully documented in the electronic case report form (eCRF) and source documents and the patient followed by the investigator/investigative staff. Even after the study is completed at the Follow-up Visit, the investigator/investigative staff will, regardless of reason for withdrawal, record any patient data they receive concerning SAEs, and all drug-related non-serious AEs, and subsequently report these to Albireo. Withdrawn patients will not be replaced.

Patients will be withdrawn in the following circumstances:

- A patient's/caregiver's desire for withdrawal for any reason
- Lost to follow-up (every effort must be made to contact the patient/caregiver; a certified letter must be sent)
- An AE that, in the opinion of the investigator, necessitates withdrawal
- A worsening of the symptoms related to diarrhea occurs
- Death
- Patient/caregiver estimation of lack of improvement/intolerable symptoms
- A patient's/caregiver's substantial noncompliance (eDiary and study drug compliance) or protocol violation
- An investigator's opinion that continuing the patient in the study is not appropriate. The investigator may withdraw a patient at any time, if it is considered to be in the patient's best interest

A patient who prematurely withdraws due to no improvement/intolerable symptoms, and has completed at least 12 weeks treatment in the double-blind study, will be offered the opportunity to enter open-label Study A4250-008. A patient who withdraws from treatment prematurely and will not enter Study A4250-008 will be requested to complete all visits and safety assessments per the current protocol (A4250-005). As a minimum, patients will have EOT (Visit 9) assessments at the time of withdrawal and a follow-up assessment (Visit 10) 28 days following the last dose of study drug, and the patient will be recorded as withdrawn.

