### **5.3.1 Risk/Benefit**

A4250 has been evaluated in three Albireo-sponsored clinical studies: a double-blind placebo-controlled study in healthy volunteers, a single-dose ADME study, and a Phase 2 study in children with cholestatic pruritus. In addition, an investigator-sponsored study has been conducted in patients with PBC.

A total of 98 subjects/patients have been exposed to A4250. Healthy subjects have been exposed to up to 10 mg as a single dose and up to 3 mg daily as part of a multiple-dose evaluation. Children with cholestatic liver disease have been treated with up to 0.2 mg/kg/day (200 µg/kg/day) for 4 weeks. In total, 2 SAEs have been reported; both were judged by the physician to be not related to the study drug.

Patients with cholestatic liver diseases suffer from excess bile acids in the liver resulting in tissue damage. A commonly used treatment in these patients is bile diversion surgery, whereby approximately 50% to 100% of the enterohepatic circulation of bile acids is interrupted. Inhibition of IBAT with A4250, thereby interrupting the enterohepatic circulation of bile acids, is therefore a potential medical alternative to surgery which could be of benefit to these patients if shown to be effective and safe. Data from the Phase 2 study showed efficacy of A4250 in reducing s-BA concentrations and pruritus in such patients.

Based on the mode of action of an IBAT inhibitor, loose stools or diarrhea could be expected. However, in the pediatric Phase 2 study with 4 weeks daily treatment, only one patient had mild transient diarrhea after a single dose that did not recur on multiple dosing.

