#### **10.2.2.4 Diarrhea**

Study drug should be discontinued if a patient develops diarrhea with at least 1 of the following concomitant signs or symptoms: grossly bloody stools, vomiting, dehydration

requiring treatment with oral or intravenous rehydration and/or electrolyte imbalances, fever ( $\geq 38$  C) and/or the diarrhea persists for 7 or more days.

If there is gross blood in stool, INR and platelets should be measured.

Study drug will be reintroduced (re-challenge) when the symptoms have resolved. If the diarrhea re-occurs within 1 week after the re-challenge with no alternate etiology, the patient will be permanently discontinued and monitored as outlined in [Section 10.2.2.5](#).

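### For a child whose diarrhea worsens, Section 7.2.3 requires withdrawal while Section 10.2.2.4 requires interruption and re-challenge

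*Protocol*

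**What the plan says.** Section 7.2.3 opens its list with "Patients will be withdrawn in the following circumstances". The bullet on adverse events leaves the decision to the physician: "An AE that, in the opinion of the investigator, necessitates withdrawal". The next bullet reads "A worsening of the symptoms related to diarrhea occurs". It names no grade or duration, does not mention the investigator's opinion, and does not refer to Section 10.2.2.4. The same section states "Withdrawn patients will not be replaced". A withdrawn patient has at least the end-of-treatment assessments and Visit 10, and is recorded as withdrawn.

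Section 10.2.2.4 sets a stepwise rule:

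- Stopping: "Study drug should be discontinued if a patient develops diarrhea with at least 1 of the following concomitant signs or symptoms". The list covers blood in the stool, vomiting, treated dehydration, electrolyte imbalance and fever. Diarrhea lasting 7 days or more also qualifies.
- Restarting: "Study drug will be reintroduced (re-challenge) when the symptoms have resolved".
- Stopping for good: "If the diarrhea re-occurs within 1 week after the re-challenge with no alternate etiology, the patient will be permanently discontinued".

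Section 5.3.1 says that, given how the drug works, "loose stools or diarrhea could be expected".

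**The concern.** The two sections cover the same foreseeable event and lead to different outcomes. A site that follows 7.2.3 ends the child's participation on drug. A site that follows 10.2.2.4 interrupts drug, waits for recovery and restarts it. Both outcomes are worded as things that will happen, so a site cannot tell which to apply.

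What is at stake is mainly conduct. Children could lose treatment that the protocol's own clinical rule would have kept them on, and the same event could be handled differently from site to site. Because diarrhea is expected from the mode of action, such withdrawals might fall more often in the active arms. Three features of the protocol add some weight:

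- Withdrawn patients are not replaced.
- Early entry to the extension study is offered only to patients who leave for lack of improvement or intolerable symptoms after at least 12 weeks. A child withdrawn for diarrhea before week 12 therefore has no stated route to open-label drug.
- The Cochran-Mantel-Haenszel sensitivity analysis in Section 11.2.2.5 counts dropouts as non-responders, so withdrawals that depend on the site could reach that result.

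**Working it through.** No calculation decides this point, so the check sets the two rules side by side. Take a child with mild diarrhea on study drug that worsens to include vomiting.

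| Step | Section 7.2.3 | Section 10.2.2.4 |
|---|---|---|
| Is the rule triggered? | Yes: diarrhea symptoms have worsened | Yes: diarrhea with a listed feature |
| Immediate action | Withdraw; end-of-treatment assessments | Stop study drug |
| After symptoms resolve | No route back to drug; Visit 10; recorded as withdrawn | Drug is restarted |
| When the stop is permanent | At once | Only on recurrence within 1 week of restarting, with no other cause found |

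The third row is where the sections part: a child who has been withdrawn cannot be re-challenged.

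**Is there a precedence rule?** Neither section refers to the other on this point, and no text in the file says which governs.

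**How far does the conflict reach?** Diarrhea that meets the 10.2.2.4 criteria from the outset is not clearly a worsening. A failed re-challenge ends in permanent discontinuation under 10.2.2.4, so the two sections do not clash there. Worsening that stays below the 10.2.2.4 criteria is also left out: 10.2.2.4 is silent there, and silence is not a contradiction. What remains is existing diarrhea that worsens into the criteria.

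**Which text was compared?** The file holds two copies of the 06 December 2017 text that show both sections, and both copies contain the conflict. It also holds the later part of a further copy. That copy's 10.2.2.4 has the same re-challenge rule, but its 7.2.3 is not in the file.

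**Where did the bullet come from?** The superseded 20 September 2017 version already has it in its withdrawal section (7.3.3). The contents of that version list liver monitoring at 10.2.2 and no diarrhea section. The bullet therefore appears to have been carried over unchanged when 10.2.2.4 was written. This explains the likely origin only; the conflict lies wholly within the December text.

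**Scale.** Section 11.1 plans about 20 patients per group, so one withdrawn patient is 1/20 = 5% of an arm. This says nothing about how likely the event is.

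**The case against.** Four arguments can be made on the other side.

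**The bullet can be read more narrowly.** Worsening presupposes existing diarrhea, so the bullet might be meant for deterioration after the 10.2.2.4 steps have been tried. Vomiting or fever might also count as an accompanying sign and not as a worsening of the diarrhea. A site would normally let the detailed rule override a loose bullet. These readings are sensible, but the protocol states none of them, and the literal reading remains open.

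**The list is not self-executing.** The same opening words also cover protocol violations, yet Section 13.1 says only that deviations may lead to withdrawal, and the last bullet says the investigator may withdraw a patient. That is fair as a comment on style. Even so, the investigator-opinion and best-interest bullets are separate grounds that add reasons to withdraw; they do not qualify the diarrhea bullet.

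**The consequences are small and partly covered.** Patients who stop treatment and do not enter the extension are asked to complete all visits, and Section 11.2.2.2 provides for continued efficacy data after discontinuation. Section 11.1 aims to enroll 60 to 70 patients to obtain at least 60 evaluable, which leaves up to 70 − 60 = 10 patients of margin across three arms. Phase 2 saw one mild transient case that did not recur. All of this stands, and it is why the point is rated minor and claims no loss of power.

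**The version in force is not established.** This also stands. If a later version changed the bullet, the point falls away.

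**Conclusion.** The concern holds. In the December 2017 text, the 7.2.3 bullet is wrong as written: followed literally, it withdraws a child whom 10.2.2.4 would return to study drug, and nothing resolves the difference. Severity is minor. No hypothesis test, error rate or sample-size figure is affected. The number of children involved is unknown and may be small. Any excess in the active arms is plausible from the mode of action, but no comparative rate in the document supports it. Confidence is medium, because the conclusion assumes that the bullet still stands in the version in force, which the file does not show.

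**What to change.** First confirm that the bullet is present in the version in force. If it is, replace it with: *Permanent discontinuation of study drug for diarrhea per Section 10.2.2.4*. Keep the adverse-event and best-interest grounds in 7.2.3, so that an investigator can still withdraw a child earlier where safety calls for it. No safety protection is lost, because 10.2.2.4 still stops drug on its own criteria. The cost is one line of protocol text and a short clarification to sites.
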